It also covers patients who had been registered to a special drug use investigation, SDUI (Protocol No.204524) for bronchial asthma, but had a change in treatment purpose from bronchial asthma to EGPA during the observation period.

* : Irrespective of whether patients have a history of Nucala treatment for bronchial asthma or not

4. Target Sample Size and Rationale

Target number of patients: 300 patients (as a safety analysis population)

Rationale:

In a phase III international joint study conducted in EGPA patients (mepolizumab group: 68 patients), the incidence of serious infection defined as the important potential risk was 5.88% (4/68 patients). On the assumption that the incidence used as a threshold is 6%, to confirm that the lower bound of the two-sided 95% CI exceeds the 6% threshold when the real risk exists two times or more, 277 patients are required as a safety analysis population. Accordingly, the target number of patients was set at 300 in consideration of the dropouts.

5. Planned Number of Medical Institutions by Department

All medical institutions where Nucala is administered to EGPA patients

6. Study Period

1. Study conduct

Study period: from the approval of EGPA indication to three months after termination of the observation period in patients eligible for case report form (CRF) collection (period of the follow-up investigation, if conducted) or the lifting of approval conditions, whichever comes later

Observation period: The observation period per patient is up to 96 weeks (2 years) from the start of Nucala administration for EGPA at a maximum. If a patient has withdrawn from/terminated administration of Nucala, it will be until the withdrawal/termination. Additionally, to consider the safety and effectiveness of Nucala administration in patients who had withdrawn from/terminated due to “symptom improvement”, the 48-week (1-year) follow-up investigation should be conducted as much as possible.

Scheduled enrolment period: from the approval of EGPA indication to the lifting of approval condition

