- 2) After the approval of EGPA indication, the Written Contract should be concluded before the start of administration in principle, however, patients to whom Nucala has unavoidably been administered before the conclusion of the contract will also be enrolled as a retrospective patient.
4. Data collection and case report form (CRF) completion
 - 1) The investigator will confirm the study items, such as the characteristics of patients eligible for CRF collection.
 - 2) During the observation period, the investigator will monitor the information about safety and effectiveness, etc.
 - 3) At the end of the observation period of patients eligible for CRF collection (or at withdrawal/termination, if a patient has withdrawn from/terminated administration of Nucala), the investigator will record the obtained information on the CRF and submit the completed CRF to the person in charge of this study. The personally identifiable information, such as the name, address, date of birth, initials of patients, should not be recorded in the CRF.
5. Confirmation of all-case investigation implementation
Annually and after the end of the study period, the investigator will confirm whether or not enrolled patients are all receiving Nucala, affix his/her signature or name/seal to the “Confirmation Letter of All-Case Investigation” and submit it to the person in charge of this study.
6. Obtaining Informed Consent
The investigator will provide a patient eligible for CRF collection (and/or, his/her substitute) with a full explanation on the publication of the study results either verbally, or in writing using an informed consent form and obtain informed consent.

8. Study Items

The investigator will collect the information about the following items, etc. as far as possible and record it on the CRF.

1. Information on medical institution
Name of a medical institution, department, investigator
2. Patient characteristics (at the start of Nucala administration for EGPA (hereinafter referred to as “at the start of Nucala administration”))

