If a patient has bronchial asthma as a comorbidity, frequency of exacerbation of bronchial asthma which corresponds to the either types defined below and a total number of days patient hospitalized for bronchial asthma treatment from 48 weeks prior to the initiation of Nucala treatment to Weeks 12, 48 and 96 after the administration (or to the time point of withdrawal/termination);
 - exacerbation of bronchial asthma which requires hospitalization
 - exacerbation of bronchial asthma which requires emergency room visit
 - exacerbation of bronchial asthma which requires usage of systemic steroids*

*The standard definitions for the usage of systemic steroids are as follows;
When a patient requires continuous administration of steroids systemically, in concrete terms, orally, intravenously or intramuscularly, for \geq three days. However, as for intramuscular injection, it must also include a continuous administration of dexamethasone phosphate acid ester sodium or betamethazoneline acid ester sodium for \geq three days, or one or more dose of triamcinolone acetonide.
When a patient requires administering systemic steroids double the existing maintenance dose for \geq three days in patients receiving the maintenance therapy of systemic steroids requiring dose increase associated with exacerbation of bronchial asthma.
Multiple exacerbation of asthma for which steroids are administered at an interval of <seven days will be handled as continuation of exacerbation of the same asthma.
12. Hospitalization for EGPA treatment
Presence or absence of hospitalization for EGPA treatment 96 weeks after the administration (or to the time point of withdrawal/termination) during the observation period, date of hospitalization and discharge if patient experienced hospitalization
13. Global assessment of effectiveness
Effectiveness will be comprehensively assessed by any of "effective" or "not effective" at Weeks 12, 48 after the start of Nucala administration, end of the observation period, or at withdrawal/termination, based on the course of subjective symptoms, course of clinical symptoms, etc. from the start date of administration to the end of the observation period. If

effectiveness cannot be determined for some reasons, it should be assessed as “indeterminable” and its reasons should be recorded on the CRF.

14. Continuation status of Nucala

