 - iii). Number of patients included in the analysis sets regarding remission and recurrence, number of patients excluded from the analysis sets and the reason for exclusion
 - 2) Safety-related matters
 - i). Occurrence of ADRs/infections (type, severity and incidence of ADRs, etc.)

- ii). Factors that potentially affect safety (occurrence of ADRs and infections by patient characteristics, etc.)
 - iii). Occurrence of events defined as a priority study matters
- 3) Effectiveness-related matters
 - i). Responder rate based on global assessment of effectiveness
The responder rate is the proportion of patients assessed as “effective”.
 - ii). Factors that potentially affect effectiveness (responder rate by patient characteristics, etc.)
 - iii). Time to EGPA remission and recurrence
The remission and recurrence are defined as follows;
 - Remission: BVAS=0 in the assessment of disease activity in systemic vasculitis assessed by 9 organ-system, 51 items.
 - Recurrence: If any of the following occurs during the observation period
 - Initiation/increased dose of adrenal cortical steroid
 - Initiation/increased dose of immune-suppressive agent
 - Hospitalization in association with the EGPA treatment
- 2. Analysis methods
Concerning the items associated with safety and effectiveness, etc., the odds ratio and 95% confidence interval will be calculated for factors that potentially affect them. These will be graphically presented using a forest plot, etc., as appropriate. For comparison of the scores, etc., the mean values and quartile points, etc. for values at the time of measurement and changes from baseline will be calculated.

10. Organizational Structure

Refer to the Attachment 1.

11. Name, Address of the Outsourcees, and the Scope of Outsourced Operations

CCI

12. Scheduled Timing to Be a Milestone for Assessing the Status and Results in the Study or Reporting to the Pharmaceuticals and Medical Devices Agency (PMDA) and Rationale

- At the time of Periodic Safety Reports: consideration will be comprehensively given to the safety and effectiveness information.
- At the time of re-examination application: the final report will be prepared/submitted, based on the results of tabular analysis obtained from the fixed data of all collected CRFs.

13. Additional Measures that Have a Potential to Be Taken Depending to the Study Results and the Decision Criteria for the Start

The RMP, including the following, will be reviewed at the timings to be a milestone.

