- Regarding hypersensitivity including anaphylaxis, if the proportion of occurrence, peak occurrence period and risk factors become visible as an ADR caused by Nucala, the necessity for revising the Package Insert and study materials will be considered as appropriate.
- Including whether or not a new concern in the safety specification is present, the necessity for changes in the content of plan in the study will be considered.
- The necessity for creation of the Risk Minimization Plan for a new concern in the safety specification will be considered.

14. Publication of the Study Results

The information regarding the results of the study will be provided to clinical sites as an interim report and a final report as appropriate for the purpose of “proper use” and “safety assurance”, considering a proper timing and the number of patients whose CRF is collected, etc., by means of presentation at academic conferences and papers.

In addition, the summaries of the plan and results in the study will be disclosed in GSK Clinical Study Register.

15. Other Requirements

1. Protocol revision

The progress in the study, the number of patients excluded from analysis, occurrence of unexpected/serious ADRs, large increase in occurrence of specific ADRs and validity of the study items, etc. will be timely grasped during the study period, and the Protocol will be reviewed and revised if required.

If the content of the Protocol in the study has been changed, the Change Notification should be submitted to the PMDA in advance, except for minor changes.

2. Measures to be taken in detecting issues or concerns

If issues, etc. have been detected from the results of assessment/analysis during the study period or after the completion of the study, consideration will be given on whether or not the SDUI or Post-marketing Clinical Study should be newly conducted, as appropriate.

16. Attachments

1) Organizational structure for post-marketing surveillance operations	AT1
2) NUCALA Subcutaneous Injection Special Drug Use Investigation (EGPA, long-term) Written Contract	AT2
3) NUCALA Subcutaneous Injection Special Drug Use Investigation (EGPA, long-term) Implementation Guidance	AT3
4) NUCALA Subcutaneous Injection Special Drug Use Investigation (EGPA, long-term) Enrolment Form	AT4
5) NUCALA Subcutaneous Injection Special Drug Use Investigation (EGPA, long-term) Case Report Form 1 (From the start of Nucala administration to Week 12)	AT5

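### The Week 12 and Week 48 global effectiveness ratings share an evidence window that runs to the end of observation, so early ratings could be influenced by later outcome

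*Combined protocol and SAP*

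**What the plan says.** Section 8, item 13 schedules the global rating "at Weeks 12, 48 after the start of Nucala administration, end of the observation period, or at withdrawal/termination". The basis for the judgement is the course of subjective and clinical symptoms "from the start date of administration to the end of the observation period". No shorter window is given for the earlier ratings, and the item lists no date of rating.

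Section 6 sets the length of that window: "The observation period per patient is up to 96 weeks (2 years) from the start of Nucala administration for EGPA at a maximum". For a patient who stops, observation ends at withdrawal or termination.

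Section 7.4, item 2 covers the period itself: "During the observation period, the investigator will monitor the information about safety and effectiveness, etc". Item 3 then gives the only stated time for recording: "At the end of the observation period of patients eligible for CRF collection", or at withdrawal/termination, "the investigator will record the obtained information on the CRF and submit the completed CRF to the person in charge of this study".

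Section 16 lists three period-specific forms. The first is "Report Form 1 (From the start of Nucala administration to Week 12"; the next two cover Weeks 13-48 and Weeks 49-96. The body of the protocol does not say when each is to be completed.

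Section 9.1, item 3) i) lists "Responder rate based on global assessment of effectiveness" as the first effectiveness analysis. It defines the rate as the proportion rated effective and names no time point. Section 9.2 plans odds ratios with 95% confidence intervals for factors that may affect effectiveness, also without a time point.

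**The concern.** A Week 12 rating should summarise the course up to Week 12. The text tells the investigator to consider the course to the end of observation, and the only recording step it describes falls at that end. An investigator who follows both instructions would fill in the Week 12 and Week 48 ratings knowing how the patient eventually did.

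The rating is a subjective judgement with no control group, so hindsight can enter easily and could not be detected from the listed items. Any Week 12 or Week 48 responder rate, and any odds ratio built on it, would then mix early effect with later outcome. A comparison across Weeks 12, 48 and 96 would show less change over time than really occurred.

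**Working it through.** The plan gives no response rate, so there is no figure to reproduce. The check is a comparison of sections, followed by an illustration on assumed values.

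**1. How much later course the stated window admits** (section 8, item 13 with section 6), for a patient observed for the full 96 weeks:

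- Week 12 rating: 96 - 12 = 84 weeks lie after the rating time, or 84/96 = 87.5% of the window.
- Week 48 rating: 96 - 48 = 48 weeks, or 50%.
- End-of-observation rating: 0 weeks.
- Rating at withdrawal: 0 weeks, because observation ends there.

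The mismatch is confined to the two early ratings. A patient who withdraws at, say, Week 60 has a sound withdrawal rating but the same problem with the Week 12 and Week 48 ratings.

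**2. Whether neighbouring items use the same form of window.** Section 8, item 11 (asthma exacerbations) counts up to Weeks 12, 48 and 96, or to withdrawal, so it ends at each time point. Item 10 (clinical symptoms) collects a date of assessment. Item 13 does neither.

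**3. When the ratings are recorded.** Section 7.4, item 3 points to the end of observation or withdrawal. The three forms in section 16 point to period-by-period recording. The form contents and the Implementation Guidance (attachment 3) are not in the text, so the conflict cannot be settled from the documents. Section 7.3, item 2) also admits patients treated before the contract. Depending on the delay, some of their early ratings may have been made in hindsight whichever reading applies.

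**4. Direction of any shift (assumed values only).** Let p be the true Week 12 rate, r the fraction of early responders later judged not effective, and g the fraction of early non-responders later judged effective. If the Week 12 rating rests entirely on the full course:

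recorded rate = p(1 - r) + (1 - p)g

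Taking r from 5% to 20% and g from 0 to 40%:

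- p = 60%, lowest: 0.60 × 0.80 + 0.40 × 0 = 48% (12 points down).
- p = 60%, highest: 0.60 × 0.95 + 0.40 × 0.40 = 73% (13 points up).
- p = 80%, lowest: 0.80 × 0.80 + 0.20 × 0 = 64% (16 points down).
- p = 80%, highest: 0.80 × 0.95 + 0.20 × 0.40 = 84% (4 points up).

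The sign depends on the balance of late gains and late losses, which the documents do not give.

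**5. What can still be changed.** CRF collection covers patients starting by 31 October 2019 (section 6). Adding 96 weeks (672 days) gives 2 September 2021. This version is dated 23 July 2024, and final analysis is due in July 2025. For that cohort the ratings are already made. New wording can reach only CRFs collected as required from patients starting on or after 1 November 2019.

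**The case against.** The strongest reply is that the ratings are specified to be made at Weeks 12 and 48, when later course is unknown, and that effectiveness is monitored throughout. On that reading the closing phrase loosely describes the final rating, or the whole span over which ratings are made, and the period-specific forms fit timely recording. This stands as a possible reading. It means hindsight is permitted by the text but not shown to have occurred.

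A second reply is that section 9 names no time point, so no Week 12 or Week 48 rate or odds ratio is explicitly planned. It names no primary effectiveness endpoint either, and the sample size rests on serious infection. That also stands: early rates are implied by the rating schedule and no more. It is a reason to name the time points, since as written nothing prevents an early rate from being reported without qualification.

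A reader might infer that all CRFs are completed only at the end and that early rates are therefore contaminated. Section 16 leaves the first step open, so the second does not follow. A reader might also suppose a one-sided bias, for example 20 points if response rose from 60% to 80%, and set it against a confidence-interval half-width of about 6 points (1.96 × √(0.6 × 0.4/277) = 0.058). Neither response rate is in the documents, the shift can go either way, and 277 is the safety sample size. The size of the effectiveness set is not stated.

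**Conclusion.** The wording defect is real. Section 8, item 13 attaches a window of up to 96 weeks to ratings due at Weeks 12 and 48, and section 7.4 and section 16 disagree on when the ratings are recorded. Early ratings could therefore be influenced by later outcome. The amount and direction cannot be estimated from the documents; the ranges above rest wholly on assumed re-rating fractions and on the extreme case in which every early rating used the full course. The ratings at the end of observation and at withdrawal are sound on this point, and the safety objective is not touched. The point should be corrected because the correction is small and the affected outcome is the first-listed effectiveness item.

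**What to change.** - **Section 8, item 13:** end each rating's window at the time point being assessed (Week 12, Week 48, end of observation or withdrawal), in the manner of item 11.
- **Section 7.4, item 3:** align completion of CRF 1, 2 and 3 with each form's own window, so that the text agrees with section 16.
- **Section 9:** name the time point or points of the responder rate. Use the end-of-observation or withdrawal rating for the headline rate and the odds ratios.
- **CRFs already collected:** where completion or receipt dates are held, flag Week 12 and Week 48 ratings recorded late and repeat any early responder analysis without them. Where dates are not held, or few timely ratings remain, report the early rates as possibly reflecting later course.

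The cost is three wording changes and one additional table; the form structure already exists. The rewording helps only later-collected CRFs, so most of the benefit lies in the analysis and reporting steps. The re-analysis depends on dates that item 13 does not list. If section 7.4 was followed literally, few timely early ratings will remain, mainly from patients who withdrew soon after the time point in question. Early rates from that subset may be imprecise and unrepresentative, and the report should say so.

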Identification number, gender, year of birth or age at the start of Nucala administration, start date of Nucala administration, presence and absence of obtained informed consent regarding study result publication, body weight, reasons for use of Nucala, date (month, year) of EGPA diagnosis, severity classification of EGPA^{*1} at the start of Nucala administration, presence or absence of hospitalization due to EGPA in 48 weeks before the start of Nucala administration and number of times patient experienced hospitalization, presence and absence of past

medical history/comorbidity (bronchial asthma, renal impairment, hepatic function abnormal, others) and name of disease, presence or absence of history of Nucala use for bronchial asthma if a patient has comorbid bronchial asthma.

To protect the confidentiality regarding identification of an individual patient, the identification number should be a unique number assigned to an individual patient by the investigator, etc.

In this study, any disease, symptom, and allergy history other than EGPA which is present before the start of administration of Nucala but has recovered/resolved by the start of Nucala administration will be handled as a “past history”. Meanwhile, any disease, symptom, and allergy other than EGPA which is present at the start of Nucala administration will be handled as a “comorbidity”.

*1 : Severity Classification of EGPA defined by Japan Intractable Diseases Information Center (Japan Intractable Diseases Research Foundation)

3. Administration status of Nucala
Single dose during the observation period (mg/dose), daily dose frequency (X times per day), administration date, reasons for revision of dosage and administration
4. Pre-treatment medications (during 4 weeks before the start of Nucala administration) and concomitant medications (adrenal cortical steroid (including medications for bronchial asthma), immune-suppressive agent and immunoglobulin preparations only)
Presence or absence of adrenal cortical steroid (including medications for bronchial asthma), immune-suppressive agent and immunoglobulin preparations during 4 weeks before the start of Nucala administration and during the observation period, name of drugs, daily dose, start date of administration, end date of administration, reasons for administration
5. Concomitant medications (other than adrenal cortical steroid, immune-suppressive agent and immunoglobulin preparations)

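### Recurrence needs no prior remission and its drug components are not limited to EGPA, so the plan reports time to first escalation or EGPA hospitalization as EGPA recurrence

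*Combined protocol and SAP*

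**What the plan says.** Section 9, item 1, 3) iii) lists "Time to EGPA remission and recurrence" among the effectiveness analyses and defines both terms. The first reads "Remission: BVAS=0 in the assessment of disease activity in systemic vasculitis assessed by 9 organ-system, 51 items". The second reads "Recurrence: If any of the following occurs during the observation period", followed by three components: "Initiation/increased dose of adrenal cortical steroid", "Initiation/increased dose of immune-suppressive agent" and "Hospitalization in association with the EGPA treatment".

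Section 6 sets the observation period. It opens at the first Nucala dose given for EGPA and runs for at most 96 weeks, or until treatment ends.

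Under patient disposition, section 9, item 1, 1) iii) asks for "Number of patients included in the analysis sets regarding remission and recurrence", with exclusions and their reasons. It does not say who belongs to those sets. Section 9, item 2 names odds ratios with 95% confidence intervals and summary statistics for scores. It gives no time origin, risk set, censoring rule or time-to-event method for this endpoint.

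On data, section 8, item 4 covers steroids (those for asthma expressly included), immunosuppressants and immunoglobulins. It records "name of drugs, daily dose, start date of administration, end date of administration, reasons for administration".

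**The concern.** A reader of a paired remission and recurrence analysis will take recurrence to mean the return of EGPA activity after it had gone. The stated rule does not say that. Its window opens at first dose rather than at remission, and no section adds a remission condition. Only the hospitalization component is tied to EGPA; the steroid and immunosuppressant components count whatever the reason for the change.

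The results go into the final report for the re-examination application (section 12) and into conference presentations and papers (section 14). A curve labelled recurrence that mixes relapse, disease that never came under control and steroid courses for asthma could be misread in either setting.

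**Working it through.** The plan gives no remission rate, recurrence rate or event count, so there is no figure to reproduce. The check is mainly to apply the rule as written.

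**Step 1. Four hypothetical patients.**

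| Patient | Rule as written | Relapse of EGPA after remission? |
|---|---|---|
| A: never reaches BVAS=0; steroid increased at Week 4 | Recurrence at Week 4 | No, never remitted |
| B: steroid increased at Week 4; first BVAS=0 at Week 12 | Recurrence at Week 4, remission at Week 12 | No, the event comes before remission |
| C: BVAS=0 from the start; steroid course for asthma only | Recurrence | No, the drug change was not for EGPA |
| D: BVAS=0 at Week 12; steroid increased for EGPA at Week 36 | Recurrence | Yes: 36 weeks from first dose, or 36 − 12 = 24 weeks from remission |

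Patient C follows from the plan's own classification. Section 8, item 2 records bronchial asthma as a past history or comorbidity, defined there as a disease other than EGPA. Section 8, item 11 counts an asthma exacerbation when systemic steroids are needed for at least three days, or when a maintenance dose is doubled for that long. A doubled dose is an increased dose, so it also meets the steroid component of recurrence.

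**Step 2. Can the analysis set remove the problem?** An unstated membership rule could exclude patient A. It could not correct B, who did remit and would belong to any set of ever-remitted patients while still carrying an event dated before remission. Nor could it correct C. Order of events and reason for the drug change are properties of the event definition, not of set membership.

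**Step 3. Are the data there?** Drug doses, dates and reasons are in section 8, item 4. Dated symptom assessments at the start and every 12 weeks to Week 96 are in item 10, and EGPA hospitalization dates in item 12. A remission-anchored endpoint can be derived without new collection.

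**Step 4. Size, on assumed inputs only.** Let m be the share who ever remit, pR the event risk in remitters and pN the event risk in never-remitters.

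- Share with recurrence as written, over all patients: m·pR + (1−m)·pN
- Share among remitters: pR
- Never-remitters' share of counted events: (1−m)·pN / [m·pR + (1−m)·pN]

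| m | pR | pN | As written | Among remitters | Never-remitters' share of events |
|---|---|---|---|---|---|
| 0.7 | 0.2 | 0.2 | 0.14 + 0.06 = 20% | 20% | 0.06/0.20 = 30% |
| 0.5 | 0.2 | 0.6 | 0.10 + 0.30 = 40% | 20% | 0.30/0.40 = 75% |
| 0.3 | 0.2 | 0.8 | 0.06 + 0.56 = 62% | 20% | 0.56/0.62 = 90% |
| 0.3 | 0.4 | 0.8 | 0.12 + 0.56 = 68% | 40% | 0.56/0.68 = 82% |

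Over m = 30–70%, pR = 20–40% and pN from pR up to 80%, the written rule gives 20–68%, against 20–40% among remitters. Never-remitters supply 30–90% of counted events. The two proportions have different denominators. They coincide when pN = pR, and the written rule would give the lower figure if pN were below pR. The illustration leaves out patients like B and C.

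**The case against.** The case for leaving the text alone has four parts.

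- **Analysis sets.** Dedicated sets exist, and their rule may exclude patients who never remit. This stands to the extent that one cannot assert such patients will appear in the reported curve. It does not rescue the definition, because events before remission and non-EGPA drug changes would remain.
- **Nothing is miscalculated.** This is a descriptive investigation without a comparison group, and it has no hypothesis or decision rule on recurrence. Time from first dose to first escalation or EGPA hospitalization is a legitimate quantity. This stands. A reader might infer that the time-to-recurrence result is wrong; the documents support only that it is mislabelled.
- **Purpose.** No section says the analysis is meant to measure durability of remission. This also stands: that purpose is inferred from the pairing and the word recurrence.
- **Timing and precision.** Patients whose CRFs are required started by 31 October 2019, so their 96 weeks ended in 2021, whereas this protocol version is dated July 2024. A redefinition now would be post hoc for them. Remission is seen only at roughly 12-week assessments, collected as far as possible. An event after true remission but before its first recorded assessment would be classed as occurring without remission. Both points stand as costs to disclose. They do not argue for keeping the label.

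**Conclusion.** The point holds as a mislabelled endpoint. As written, the rule measures time to first steroid or immunosuppressant escalation or EGPA hospitalization from first dose, and calls it EGPA recurrence. This rests on the text alone: no prior BVAS=0 is required, and the drug components have no EGPA condition.

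Its size is unknown. The ranges above show only that the effect could run from no difference in the overall proportion to a large one. Even with equal proportions, some counted events would not be relapses. A reader might infer that recurrence is overstated by a definite amount, but neither the amount nor the direction can be derived from the documents. It should be settled before the results are reported as recurrence.

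**What to change.** 1. Limit the steroid and immunosuppressant components to changes whose recorded reason is EGPA.
2. Define the recurrence set as patients with a recorded BVAS=0, at the start or on treatment. Start the clock at that assessment date (or at first dose if a baseline assessment preceded it) and count only later events. State the censoring rule.
3. Report the event in all patients from first dose separately, named *time to first steroid/immunosuppressant escalation or EGPA hospitalization*.
4. Label the change as made after data collection if that is so, and note that remission dates are known only to the assessment interval.
5. Reconcile the BVAS item sets: section 8, item 10 collects 56 items, while the remission definition in section 9 refers to 51. The BVAS=0 condition depends on which set is used.

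The cost is revised wording and a derivation from data already collected, plus advance notification to the PMDA under section 15 unless the change counts as minor. The statistical downside is fewer patients and events in the recurrence curve. Keeping the all-patient quantity under item 3 means no information is lost.
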